8.3.2.1 HOSPITALIZATION

For reports of hospitalization, it is the sign, symptom or diagnosis which led to the hospitalization that is the serious event for which details must be provided.

Any event requiring hospitalization or prolongation of hospitalization that occurs during the study must be reported as a serious adverse event, except hospitalizations for the following:

- Hospitalizations not intended to treat an acute illness or adverse event (e.g., social reasons such as pending placement in long-term care facility)
- Surgery or procedure planned before entry into the study. [Note: Hospitalizations that were planned before the start of data collection and where the underlying condition for which the hospitalization was planned has not worsened will not be considered serious adverse events. Any adverse event that results in a prolongation of the originally planned hospitalization is to be reported as a new serious adverse event.]

8.3.3 CLASSIFICATION OF AN ADVERSE EVENT

8.3.3.1 SEVERITY OF EVENT

For adverse events (AEs) not included in the protocol defined grading system, the following guidelines will be used to describe severity.

- **Mild** – Events require minimal or no treatment and do not interfere with the participant's daily activities. [Equivalent to National Cancer Institute (NCI) Common Terminology Criteria for Adverse Events (CTCAE) Grade 1]

- **Moderate** – Events result in a low level of inconvenience or concern with the therapeutic measures. Moderate events may cause some interference with functioning. [Equivalent to NCI CTCAE Grade 2]
- **Severe** – Events interrupt a participant’s usual daily activity and may require systemic drug therapy or other treatment. Severe events are usually potentially life-threatening or incapacitating. [Equivalent to NCI CTCAE Grade 3 or higher] Of note, the term “severe” does not necessarily equate to “serious”.

8.3.3.2 RELATIONSHIP TO STUDY INTERVENTION

All adverse events (AEs) must have their relationship to study intervention assessed by the clinician who examines and evaluates the participant based on temporal relationship and his/her clinical judgment. The degree of certainty about causality will be graded using the categories below. In a clinical trial, the study product must always be suspect.

- **Related** – The AE is known to occur with the study intervention, there is a reasonable possibility that the study intervention caused the AE, or there is a temporal relationship between the study intervention and event. Reasonable possibility means that there is evidence to suggest a causal relationship between the study intervention and the AE.
- **Not Related** – There is not a reasonable possibility that the administration of the study intervention caused the event, there is no temporal relationship between the study intervention and event onset, or an alternate etiology has been established.

8.3.3.3 EXPECTEDNESS

The investigator will be responsible for determining whether an adverse event (AE) is expected or unexpected. An AE will be considered unexpected if the nature, severity, or frequency of the event is not consistent with the risk information previously described for the study intervention.

An adverse event is considered unlisted if the nature or severity is not consistent with the applicable product reference safety information. For a medicinal product(s) with a marketing authorization, the expectedness of an adverse event will be determined by whether or not it is listed in the applicable product information.

<http://www.darzalex.com/shared/product/darzalex/darzalex-prescribing-information.pdf>

For daratumumab, the expectedness of an adverse event will be determined by whether or not it is listed in the Investigator's Brochure.

8.3.4 TIME PERIOD AND FREQUENCY FOR EVENT ASSESSMENT AND FOLLOW-UP

The occurrence of an adverse event (AE) or serious adverse event (SAE) may come to the attention of study personnel during study visits and interviews of a study participant presenting for medical care, or upon review by a study monitor.

All AEs including local and systemic reactions not meeting the criteria for SAEs will be captured on the appropriate case report form (CRF). Information to be collected includes event description, time of onset, clinician's assessment of severity, relationship to study product (assessed only by those with the training and authority to make a diagnosis), and time of resolution/stabilization of the event. All AEs occurring while on study must be documented appropriately regardless of relationship. All AEs will be followed to adequate resolution.

Any medical condition that is present at the time that the participant is screened will be considered as baseline and not reported as an AE. However, if the study participant's condition deteriorates at any time during the study, it will be recorded as an AE.

Changes in the severity of an AE will be documented to allow an assessment of the duration of the event at each level of severity to be performed. AEs characterized as intermittent require documentation of onset and duration of each episode.

The investigator or study coordinator will record all reportable events with start dates occurring any time after informed consent is obtained until 7 (for nonserious AEs) or 30 days (for SAEs) after the last day of study participation. At each study visit, the study staff will inquire about the occurrence of AE/SAEs since the last visit. Events will be followed for outcome information until resolution or stabilization.

All serious adverse events that have not resolved by the end of the study, or that have not resolved upon discontinuation of the subject's participation in the study, must be followed until any of the following occurs:

- The event resolves
- The event stabilizes
- The event returns to baseline, if a baseline value/status is available
- The event can be attributed to agents other than the study drug or to factors unrelated to study conduct
- It becomes unlikely that any additional information can be obtained (subject or health care practitioner refusal to provide additional information, lost to follow-up after demonstration of due diligence with follow-up efforts)

Maintenance of Safety Information:

All safety data should be maintained in a clinical database in a retrievable format. The Principal Investigator shall provide all adverse events, both serious and non-serious, in report format. However, in certain circumstances more frequent provision of safety data may be necessary, e.g. to fulfill a regulatory request, and as such the data shall be made available within a reasonable timeframe at Janssen Scientific Affairs, LLC request.

8.3.5 ADVERSE EVENT REPORTING

All adverse events (AEs) will be recorded in the Case Report Form (CRF), and will be reviewed on an ongoing basis by the investigator and the Independent safety monitor. The Principal Investigator shall

be solely responsible for complying, within the required timelines, with any safety reporting obligation to competent Health Authorities and the IRB, as defined in applicable laws and regulations. For the purposes of this section, safety data includes adverse events, product quality complaints (PQCs), and special situations including pregnancies. The Principal Investigator will provide safety information to Janssen Scientific Affairs, LLC on adverse events, special situations including pregnancies and product quality complaints as defined within this section. This study has been designated as an interventional study. As such, all adverse events for Janssen Medicinal Products regardless of causality and special situations excluding those from subjects not exposed to a Janssen Medicinal Product and product quality complaints with or without an adverse event as described in this Exhibit will be reported from the time a subject has signed and dated an Informed Consent Form (ICF) until completion of the subject's last study-related procedure (which may include contact for follow-up safety). Serious adverse events will be reported for 30 days after the last dose of study drug. For the purposes of this study, the Janssen medicinal product is daratumumab. Nonserious AEs will be reported to Janssen Scientific Affairs, LLC on an annual basis. Timetables for reporting serious adverse events, events of special interest, pregnancy, and product quality complaints are detailed in the relevant sections below.

The Principal Investigator will transmit all SAEs, Adverse Events of Special Interest and special situations following exposure to a Janssen product under study in a form provided by Janssen Scientific Affairs, LLC in accordance with the Transmission Methods described below, in English within 24-hours of becoming aware of the event(s).

Transmission Methods:

The following methods are acceptable for transmission of safety information to Janssen Scientific Affairs, LLC:

- Electronically via Janssen SECURE Email service (preferred)
- For business continuity purposes, if SECURE Email is non-functional:
 - Facsimile (fax), receipt of which is evidenced in a successful fax transmission report
 - Telephone (if fax is non-functional).

Please use the contact information and process information provided by Janssen Scientific Affairs, LLC.

Dissemination of Safety Information from Janssen to Institution/Principal Investigator:

The Principal Investigator will be responsible for submitting IND safety reports for the Study Product to the Institution's IRB in accordance with Federal regulations 21 CFR 312.66.

Janssen Scientific Affairs, LLC agrees to provide to the Principal Investigator IND safety reports for the Janssen Medicinal Product as they become available until all subjects in the Protocol have completed their last Study visit according to the Protocol (i.e. Last Subject Last Visit has occurred).

For SAEs, special reporting situations and PQCs following exposure to a non-Janssen medicinal product under study, the Principal Investigator should notify the appropriate regulatory/competent authority or the manufacturer of that medicinal product (in the absence of appropriate local legislation) as soon as possible.

8.3.6 SERIOUS ADVERSE EVENT REPORTING

The study clinician will immediately report to Janssen Scientific Affairs, LLC any serious adverse event, whether or not considered study intervention related, including those listed in the protocol or Investigator's Brochure and must include an assessment of whether there is a reasonable possibility that the study intervention caused the event.

All serious adverse events (SAEs) will be followed until satisfactory resolution or until the investigator deems the event to be chronic or the participant is stable. Other supporting documentation of the event may be requested by Janssen Scientific Affairs, LLC and should be provided as soon as possible.

The Institution/Principal Investigator will be responsible for notifying the Food and Drug Administration (FDA) of any unexpected fatal or life-threatening suspected adverse reaction as soon as possible, but in no case later than 7 calendar days after the Institution/Principal Investigator's initial receipt of the information. In addition, the Institution/Principal Investigator must notify the FDA in an Investigational New Drug (IND) safety report of potential serious risks, from clinical trials or any other source, as soon as possible, but in no case later than 15 calendar days after the Institution/Principal Investigator determines that the information qualifies for reporting.

8.3.7 REPORTING EVENTS TO PARTICIPANTS

Subjects and study partners will be informed of any clinically significant incidental findings on laboratory testing or imaging studies. With appropriate written authorization from the subject or their legally authorized representative, those results can be communicated to the subject's treating physician(s). A summary of the aggregate results of the study will be provided to study participants after data analysis is complete, and will be posted on the ClinicalTrials.gov website.

8.3.8 EVENTS OF SPECIAL INTEREST

Adverse events of special interest are events that Janssen Scientific Affairs, LLC is actively monitoring as a result of a previously identified signal (even if nonserious). These adverse events are:

- Infusion reactions: \geq Grade 3
- Infections: \geq Grade 4
- Cytopenias: \geq Grade 4
- Tumor lysis syndrome
- Other malignancies
- Intravascular hemolysis – all Grades

Any Adverse Event of Special Interest that is to be reported to Janssen Scientific Affairs, LLC should be recorded on a Serious Adverse Event Report Form and be reported to Janssen Scientific Affairs, LLC within 24 hours of knowledge of the event.

Safety events of interest for a Janssen medicinal product that require expediting reporting and/or safety evaluation include, but are not limited to:

- Drug exposure during pregnancy (maternal and paternal)
- Overdose of a Janssen medicinal product
- Exposure to a Janssen medicinal product from breastfeeding
- Suspected abuse/misuse of a Janssen medicinal product
- Inadvertent or accidental exposure to a Janssen medicinal product
- Any failure of expected pharmacological action (i.e., lack of effect) of a Janssen medicinal product
- Medication error involving a Janssen medicinal product (with or without patient exposure to the Janssen medicinal product, e.g., name confusion)
- Suspected transmission of any infectious agent via administration of a medicinal product
- Unexpected therapeutic or clinical benefit from use of a Janssen medicinal product

These safety events may not meet the definition of an adverse event; however, from a Janssen Scientific Affairs, LLC perspective, they are treated in the same manner as adverse events. Special situations should be recorded on the Adverse Event page of the CRF.

Any special situation that meets the criteria of a serious adverse event should be recorded on a Serious Adverse Event Report Form and be reported to Janssen Scientific Affairs, LLC within 24 hours of becoming aware of the event.

8.3.9 REPORTING OF PREGNANCY

All initial reports of pregnancy must be reported to Janssen Scientific Affairs, LLC by the Principal Investigator within 24 hours of becoming aware of the event using the Serious Adverse Event Form. Abnormal pregnancy outcomes (e.g. spontaneous abortion, fetal death, stillbirth, congenital anomaly, ectopic pregnancy) are considered serious adverse events and must be reported using the Serious Adverse Event Form.

Any subject who becomes pregnant during the study must be promptly withdrawn from the study and discontinue further study treatment.

Because the effect of the Janssen medicinal product on sperm is unknown, pregnancies in partners of male subjects exposed to a Janssen medicinal product will be reported by the Principal Investigator within 24 hours of their knowledge of the event using the Serious Adverse Event Form. Depending on local legislation this may require prior consent of the partner.

Follow-up information regarding the outcome of the pregnancy and any postnatal sequelae in the infant will be required.

8.3.10 REPORTING OF PRODUCT QUALITY COMPLAINTS (PQC)

A product quality complaint is defined as any suspicion of a product defect related to a potential quality issue during manufacturing, packaging, release testing, stability monitoring, dose preparation, storage

or distribution of the product, or delivery system. Not all PQCs involve a subject. Lot and batch numbers are of high significance and need to be collected whenever available.

Examples of PQC include but are not limited to:

- Functional Problem: e.g., altered delivery rate in a controlled release product
- Physical Defect: e.g. abnormal odor, broken or crushed tablets/capsules
- Potential Dosing Device Malfunction: e.g., autoinjector button not working, needle detaching from syringe
- Suspected Contamination
- Suspected Counterfeit

A PQC may have an impact on the safety and efficacy of the product. Timely, accurate, and complete reporting and analysis of PQC information from studies are crucial for the protection of patients, investigators, and Janssen Scientific Affairs, LLC, and are mandated by regulatory agencies worldwide. Janssen Scientific Affairs, LLC has established procedures in conformity with regulatory requirements worldwide to ensure appropriate reporting of PQC information. Lot and/or Batch #s shall be collected on any reports failure of expected pharmacological action (i.e., lack of effect). The product should be quarantined immediately and if possible, take a picture.

All initial PQCs involving a Janssen medicinal product under study must be reported to Janssen Scientific Affairs, LLC by the Principal Investigator within 24 hours after being made aware of the event. The Janssen contact will provide additional information/form to be completed.

If the defect for a Janssen medicinal product under study is combined with either a serious adverse event or nonserious adverse event, the Principal Investigator must report the PQC to Janssen Scientific Affairs, LLC according to the serious adverse event reporting timelines. A sample of the suspected product should be maintained for further investigation if requested by Janssen Scientific Affairs, LLC.

8.4 UNANTICIPATED PROBLEMS

8.4.1 DEFINITION OF UNANTICIPATED PROBLEMS (UP)

The Office for Human Research Protections (OHRP) considers unanticipated problems involving risks to participants or others to include, in general, any incident, experience, or outcome that meets **all** of the following criteria:

- Unexpected in terms of nature, severity, or frequency given (a) the research procedures that are described in the protocol-related documents, such as the Institutional Review Board (IRB)-approved research protocol and informed consent document; and (b) the characteristics of the participant population being studied;
- Related or possibly related to participation in the research (“possibly related” means there is a reasonable possibility that the incident, experience, or outcome may have been caused by the procedures involved in the research); and

- Suggests that the research places participants or others at a greater risk of harm (including physical, psychological, economic, or social harm) than was previously known or recognized.

8.4.2 UNANTICIPATED PROBLEM REPORTING

The investigator will report unanticipated problems (UPs) to the reviewing Institutional Review Board (IRB). The UP report will include the following information:

- Protocol identifying information: protocol title and number, PI's name, and the IRB project number;
- A detailed description of the event, incident, experience, or outcome;
- An explanation of the basis for determining that the event, incident, experience, or outcome represents an UP;
- A description of any changes to the protocol or other corrective actions that have been taken or are proposed in response to the UP.

To satisfy the requirement for prompt reporting, UPs will be reported using the following timeline:

- UPs that are serious adverse events (SAEs) will be reported to the IRB and to the Independent Safety Monitor as soon as possible, but within 5 business days of the investigator becoming aware of the event.
- Any other UP will be reported to the IRB and to the Independent Safety Monitor as soon as possible, but within 5 business days of the investigator becoming aware of the problem.
- All UPs should be reported to appropriate institutional officials (as required by an institution's written reporting procedures) and the Office of the Human Research Protections (OHRP). The OHRP Director ensures that all steps of this process are completed within 30 days of the IRB decision. For more serious actions, the OHRP Director will expedite reporting. All correspondence with any federal agency will be sent on behalf and with knowledge of the Institutional Official.

8.4.3 REPORTING UNANTICIPATED PROBLEMS TO PARTICIPANTS

Subjects, study partners, and legally authorized representatives will be informed of any UPs that might affect their willingness to continue participation in the study. If the UP requires modification of the informed consent form, active subjects will be re-consented.

9 STATISTICAL CONSIDERATIONS

9.1 STATISTICAL HYPOTHESES

SPECIFIC AIM: To estimate the proportion of patients with Alzheimer's disease who respond to daratumumab.

OUTCOME VARIABLE: A patient will be considered a responder if they improve by a minimum of 4 points on the ADAS-cog/11 from baseline at 25 weeks.

STATISTICAL METHODS: The proportion of patients who respond to daratumumab will be estimated, and the associated 95% exact binomial confidence interval will be calculated.

- Primary Efficacy Endpoint:

- Responder rate defined as improvement in standard 11-item Alzheimer's Disease Assessment Scale-cognitive subscale (ADAS-cog/11) score of ≥ 4 points at 25 weeks compared with baseline

- Secondary Efficacy Endpoints:

- The proportion of subjects who are unchanged or improved from baseline at 25 weeks in ADAS-cog/12 score (standard 11 items plus delayed word recall)

- The proportion of subjects who are unchanged or improved from baseline at 25 weeks in Mini Mental State Examination (MMSE) score

- The proportion of subjects who are unchanged or improved from baseline at 25 weeks in Clinical Dementia Rating Scale Sum of Boxes (CDR-SB) score

- The proportion of subjects who are unchanged or improved from baseline at 25 weeks in ADCOMS score (a composite score derived from a weighted combination of selected items from the ADAS-cog/12, MMSE, and CDR-SB)

- Secondary Safety Endpoints:

- The proportion of subjects with one or more treatment-emergent adverse events

- The proportion of patients with one or more treatment-emergent serious adverse events

- Tertiary/Exploratory Endpoints:

- Pattern of change over time at baseline (prior to the start of daratumumab treatment), 12 weeks (midpoint), 25 weeks (endpoint), and 36 weeks (12 weeks after completion of treatment) in the following cognitive outcome measures: ADAS-cog/11, ADAS-cog/12, MMSE, CDR-SB, ADCOMS

- Change from baseline at 25 weeks in CD38 expression on circulating (whole blood) CD8+ T-cells measured with flow cytometry

- Change from baseline at 25 weeks in metabolite ratios: N-acetylaspartate/creatine (NAA/Cr), myo-inositol/creatine (mi/Cr), choline/creatine (Cho/Cr), and N-acetylaspartate/myo-inositol (NAA/mi) on single-voxel protein magnetic resonance spectroscopy from the precuneus and posterior cingulate region

9.2 SAMPLE SIZE DETERMINATION

This is a pilot study, the purpose of which is explore whether there is a clinically meaningful efficacy signal for daratumumab in patients with mild to moderate Alzheimer's disease. The proposed sample size of 15 patients is based on feasibility and availability of resources, and not on a formal power calculation.

The following table provides estimates of proportions and their associated 95% confidence intervals for a sample size of 15 subjects.

N=15			
Observed Number Responding	Observed Proportion Responding	Exact Lower 95% Confidence Interval	Exact Upper 95% Confidence Interval
0	0.000	0.000	0.218
1	0.067	0.002	0.319
2	0.133	0.017	0.405
3	0.200	0.043	0.481
4	0.267	0.078	0.551
5	0.333	0.118	0.616
6	0.400	0.163	0.677
7	0.467	0.213	0.734
8	0.533	0.266	0.787
9	0.600	0.323	0.837
10	0.667	0.384	0.882
11	0.733	0.449	0.922
12	0.800	0.519	0.957
13	0.867	0.595	0.983
14	0.933	0.681	0.998
15	1.000	0.782	1.000

For a sample size of 15 subjects, if 7 patients respond, the lower limit of the exact 95% binomial confidence interval is 0.213, (i.e., we are 95% certain that the true proportion with a response is no lower than 0.213). Based on previous results in patients with mild to moderate AD maintained on stable treatment with a cholinesterase inhibitor, the expected responder rate at 25 weeks (defined as improvement in ADAS-cog/11 score of ≥ 4 points) is 20% (0.20) (Rockwood et al. 2007). Therefore, if 7 or more of 15 subjects respond, we would consider further study of daratumumab warranted.

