9.3 POPULATIONS FOR ANALYSES

Data from all subjects who receive at least one dose of study medication will be included in all efficacy and safety analyses.

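### Does describing 0.213 as a 95% lower bound misstate the evidence behind the 7-of-15 rule?

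*Combined protocol and SAP*

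**What the plan says.** Section 9.2 tabulates exact 95% intervals, lower and upper limits together, for every possible count among 15 subjects. For 7 responders it states that "the lower limit of the exact 95% binomial confidence interval is 0.213", and then restates this in parentheses: "we are 95% certain that the true proportion with a response is no lower than 0.213". It sets that limit against an expected responder rate of 0.20, taken from earlier results in patients on a stable cholinesterase inhibitor, and concludes that "if 7 or more of 15 subjects respond, we would consider further study of daratumumab warranted".

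The planned analysis is the same interval. Section 9.1 says that "the associated 95% exact binomial confidence interval will be calculated" for the primary proportion, and section 9.4.2 repeats it. No one-sided level or one-sided limit is given anywhere in the statistical sections.

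Two other statements bear on the point. Section 9.2 says of the size: "The proposed sample size of 15 patients is based on feasibility and availability of resources, and not on a formal power calculation". Section 9.3 says: "Data from all subjects who receive at least one dose of study medication will be included in all efficacy and safety analyses".

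**The concern.** The main clause and the parenthesis are different statements. The main clause describes one end of a two-sided 95% interval. The parenthesis turns that end into a lower-bound claim at 95%, as if all of the 5% error lay below it. A one-sided 95% lower limit for 7 of 15 is a different and higher number.

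The clause links the interval to the only decision rule in the plan, so a mislabel there could leave the standard of evidence unclear: 2.5% in the lower tail, as the table implies, or 5%, as the parenthesis suggests. The rule is written for 15 subjects only. If another number were analysed, someone would have to rebuild the cutoff, and the two standards can give different answers. In an open-label single-arm study it is undesirable to settle such a choice after the results are known.

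**Working it through.** **Inputs.** n = 15, x = 7, exact binomial 95% interval, reference rate 0.20 (all section 9.2).

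**1. Reproduce the plan's figure.** The exact (Clopper-Pearson) limits are beta quantiles:

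- lower = Beta(0.025; x, n − x + 1) = Beta(0.025; 7, 9) = 0.2127
- upper = Beta(0.975; x + 1, n − x) = Beta(0.975; 8, 8) = 0.7341

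These round to the printed 0.213 and 0.734. The other 15 rows also reproduce to three decimals, so the table is two-sided throughout.

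**2. Confidence attached to 0.213 on its own.** P(X ≥ 7 | n = 15, p = 0.2127) = 0.0250. The lower-bound statement therefore has confidence 1 − 0.025 = 97.5%. The one-sided 95% limit is Beta(0.05; 7, 9) = 0.2437.

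**3. Is the parenthesis false?** Over a grid of true rates, the lowest coverage of the tabulated lower limit at n = 15 is 0.975. A bound with at least 97.5% coverage also has at least 95%. The statement is valid but understated.

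**4. Effect on the threshold at 15.**

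| Responders | Two-sided 95% lower limit | One-sided 95% lower limit | P(X ≥ count) if the rate is 0.20 |
|---|---|---|---|
| 6 | 0.163 | 0.191 | 0.0611 |
| 7 | 0.213 | 0.244 | 0.0181 |

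Six fails and seven passes under both readings: 0.0611 is above 0.05, and 0.0181 is below 0.025.

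**5. Effect at other sizes.** The documents give no expected number dosed other than 15, so this range is an assumption. The entries are the smallest counts with a lower limit above 0.20.

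| Number analysed | Two-sided 95% | One-sided 95% |
|---|---|---|
| 12 | 6 | 6 |
| 13 | 7 | 6 |
| 14 | 7 | 6 |
| 15 | 7 | 7 |
| 16 | 8 | 7 |
| 17 | 8 | 7 |

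The counts in dispute just below 15 are 6 of 14 (limits 0.177 and 0.206) and 6 of 13 (0.192 and 0.224).

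**6. Which reading does the plan support?** The sentence that contains the parenthesis names the quantity, the table prints both limits, and sections 9.1 and 9.4.2 commit to the same interval. The value 0.244 appears nowhere. Even the parenthesis attaches its certainty to 0.213, so a reader who relies on it still compares 0.213 with 0.20.

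**The case for a change.** The best case for a change is that the rule's standard of evidence is never stated separately. A single sentence naming the two-sided lower limit as the criterion, whatever the number dosed, would remove any later choice. Fifteen is only a proposed size, and sections 7.2 and 7.3 foresee withdrawal and loss to follow-up. With 14 analysed and 6 responders, the same data would miss the bar under the two-sided limit (0.177) and clear it under the one-sided limit (0.206).

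The arithmetic of that case stands, but its force is limited in three ways.

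- Section 9.3 keeps every dosed subject in the analysis, and section 7.1 asks subjects who stop dosing to return for Visits 11, 18 and 19. Leaving treatment therefore does not by itself take anyone out of the denominator; a total below 15 would come mainly from under-accrual, and section 5.5 anticipates 15. How a missing week-25 score is classified is a separate question that this wording neither raises nor settles.
- The rule is silent about other sizes because it is stated for 15. Changing 95% to 97.5% in the parenthesis would not fill that silence. An analyst who needed a cutoff at 14 would recompute the one interval that the plan specifies and would get 7.
- Printing 0.244 beside 0.213 would put a second limit into a section that now has one, and so could create the ambiguity it was meant to cure.

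**Conclusion.** The parenthesis understates its own confidence: 0.213 is a 97.5% one-sided bound described as a 95% one. The slip is conservative and confined to wording. The 16 table rows, the 0.213, the cutoff of 7 and the planned interval are all correct, and the cutoff at 15 is the same on either reading.

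The stakes are low as well. The aim is estimation, the size was set by feasibility, and the rule says only that further study would be considered; no test or error rate hangs on the phrase. The possible difference of one responder at 13, 14, 16 or 17 rests on two assumptions: a number analysed that the documents do not predict, and a one-sided criterion that they do not contain. A colleague editing section 9.2 for other reasons could drop the parenthesis without loss, but the plan does not need changing on this account.
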